4.5.7 Six-Minute Walk Test

Conduct of the 6MWT will be carefully defined and controlled according to the criteria defined and validated by du Bois et al. (2011), with additional control measures suggested in the ERS/ATS Guideline for field walking tests (Holland et al. 2014).

- The test will be performed indoors on a flat, straight corridor with a hard surface at least 30 meters in length.

- An oxygen titration procedure will be performed for patients in cohort A who require supplemental oxygen during the 6MWT (up to 6 L/min of oxygen at sea level, and up to 8 L/min at altitude [> 5000 ft]) to establish a baseline flow rate. The oxygen titration procedure should be conducted per local standard practice. Patients in Cohort B should maintain the same supplemental oxygen requirements as per study WA42293
- Before each 6MWT, patients will be required to have resting oxygen saturation as measured by pulse oximetry of at least 89% after 10 minutes of rest breathing room air, or at the baseline O₂ flow rate as established during the titration procedure.
- Patients will be instructed to walk as far as they can without jogging or running; if they need to slow down or stop to rest they will be permitted to do so and encouraged to resume walking as soon as they are able.
- The test will be stopped if the patient experiences chest pain, intolerable dyspnea, leg cramps, diaphoresis, or desaturation below 83% for at least 10 seconds.
- The pre-test conditions for oxygen use will be maintained throughout the study as much as possible, as noted at the Day 1 visit prior to first dose.

As previously described, the 6MWT assessment should be performed after PFTs, allowing for a short recovery period. In the rare instance that it is not possible to complete the 6MWT last, allow a 30–60 minute recovery time before continuing with the next efficacy assessment.

A procedure manual and training video (video instructions) detailing the testing method recommended by the ATS and the European Respiratory Society (ATS 2002; Holland et al. 2014) for the 6MWT will be provided separately. These materials will include detailed instructions for standardized execution of the 6MWT, and describe the equipment and personnel required to conduct the assessment as well as the testing methods.

The Borg Scale of Perceived Exertion ([Appendix 9](#)) will be assessed just prior to and immediately following the completion of the 6MWT.

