Appendix 1 Schedule of Activities for Cohorts A and B (cont.)

Assessment	Eligibility assessment visit ^a	Baseline /Dosing Day 1 ^{b, c}	Dosing Day 3	Dosing Day 5	Week 4, then every 4 weeks	Week 12, then every 12 weeks	Week 24, then every 24 weeks	Treatment Discontinuation ^d	Study Completion/ Discontinuation ^d
Window	4 weeks	Loading within 8 days ^e			(±5 days)	(±5 days)	(±7 days)		
Visit number	1	2	3	4					
Assessment of IPF exacerbations and hospitalizations		x	x	x	x			x	x
Spirometry		x				x		x	
6-minute walk test and Borg Scale		x				x		x	
DLco		x					x	x	
Patient Reported Outcomes; SGRQ, UCSD-SOBQ and EQ-5D-5L ^k		x					x	x	
HRCT ^l		Weeks 52 and 104 for eligible patients in Cohort B ^l							
TREATMENT ASSESSMENTS									
Study drug dosing ^m		x	x	x	x				
Adherence to pirfenidone or nintedanib	x	x	x	x	x			x	x
Lung Transplantation Assessment		x							

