5.4.1 Time-to-Event Endpoints

The time-to-event secondary endpoints are listed below:

- Time to disease progression, defined as time to first occurrence of $\geq 10\%$ absolute decline in % predicted FVC, $\geq 15\%$ relative decline in 6MWD, or death
- Survival, as measured by all-cause mortality, IPF-related mortality and respiratory-related mortality

Descriptive statistics for the frequency of each type of event will be provided. The Kaplan-Meier plot, median time to event, and their 95% CIs.

Time-to-event will be measured in reference to Baseline Day 1 of OLE study through the end of study or the time of the data-cut, whichever occurs first. For time to disease progression and survival (as measured by all-cause mortality, IPF-related mortality and respiratory-related mortality), patients without an event will be censored at the last clinic assessment.

The strategy for the time-to-event endpoints is summarized below in [Table 4](#).

Table 4 Strategy for Addressing Intercurrent Events: Time-to-Event Endpoints

Endpoint	Intercurrent Events and Strategy
Time to disease progression, defined as time to first occurrence of $\geq 10\%$ absolute decline in % predicted FVC, $\geq 15\%$ relative decline in 6MWD, or death	Any patients who undergo lung transplantation will be censored at the date of the transplant (hypothetical strategy) Any patients who withdraw from treatment will be censored at the date of last disease progression assessment, i.e., % predicted FVC and 6MWD (hypothetical strategy)
Survival, as measured by all-cause mortality, IPF-related mortality and respiratory-related mortality	Any patients who undergo lung transplantation will be censored at the date of the transplantation (hypothetical strategy) Any patients who withdraw from treatment will be censored at the date of withdrawal (hypothetical strategy)

6MWD = 6-minute walk distance; FVC = forced vital capacity; IPF = idiopathic pulmonary fibrosis.

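### Time to progression: for patients still on treatment, SAP 5.4.1 lets time without FVC and 6MWD tests count as progression-free, and Table 4 uses a different censoring date

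*SAP*

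**What the plan says.** SAP 5.4.1 has one general censoring sentence for progression and survival together: "patients without an event will be censored at the last clinic assessment". It does not define a clinic assessment or require that it include a lung function or walk test. The time window is set in the same section: "Time-to-event will be measured in reference to Baseline Day 1 of OLE study through the end of study or the time of the data-cut".

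Table 4, in the same section, gives separate rules for two intercurrent events in the progression endpoint. Patients who withdraw from treatment are "censored at the date of last disease progression assessment, i.e., % predicted FVC and 6MWD". Patients who receive a lung transplant are censored on the transplant date. The general sentence is therefore left to govern mainly patients who are on treatment and event-free at the data-cut or end of study.

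The event is a fall of at least 10 percentage points in FVC% predicted, a relative fall of at least 15% in 6MWD, or death. Protocol Appendix 1 schedules dosing visits every 4 weeks, but spirometry and the walk test only at baseline, at "Week 12, then every 12 weeks", and at the treatment discontinuation visit. Neither document says what happens to this endpoint when a scheduled test is missed.

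**The concern.** Two of the three event components can be seen only when a test is done. If an event-free patient is censored at the last attendance of any kind, the Kaplan-Meier estimate treats the time since the last test as observed and free of progression. If both tests have stopped, only death can then end that time with an event.

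Missed tests are foreseeable. Protocol 4.5.7 requires "resting oxygen saturation as measured by pulse oximetry of at least 89"% before each walk, on room air or at the baseline oxygen flow, so patients whose oxygen need rises are the likeliest to miss it. Spirometry has to reach a minimum quality to be used. Protocol 4.3.2 allows infusions away from the site in exceptional situations, and the data it lists for off-site collection do not include FVC or 6MWD.

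Time to progression is a listed efficacy endpoint, reported as Kaplan-Meier estimates with 95% confidence intervals and no control arm. An upward shift would go straight into the reported figures, and two programmers could produce different curves from the present text.

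**Working it through.** The documents give no event rate, sample size calculation or target for this endpoint, so there is no stated figure to reproduce.

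**Inputs.** From Protocol Appendix 1: visits every 4 weeks, tests every 12 weeks, a window of ±5 days. Assumed: progression 0.35 per year, death 0.08 per year, and a rate s of 5%, 10% or 20% per year at which patients lose both tests but keep attending. A year is 52.18 weeks.

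**Step 1: the scheduled gap.** The last visit falls 0, 4 or 8 weeks after the last test. One missed test round extends this to as much as 20 weeks, and it has no limit once testing stops. The scheduled gap does no harm by itself, because no test-based event can be recorded between tests. In a simulation with a 78-week median, no deaths and every test done, visit censoring and test censoring both gave 0.652 at Week 52 and 0.425 at Week 104. Complete testing followed through gave 0.653 and 0.428.

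**Step 2: the visit rule when tests stop.** Per 12 weeks:

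- probability of not progressing: p = exp(-0.35 × 12/52.18) = 0.92266, so q = 1 - p = 0.07734
- probability of still being tested: r = exp(-s × 12/52.18) = 0.98857, 0.97727, 0.95505
- probability that progression is recorded by test K: R = q·r·(1 - (p·r)^K)/(1 - p·r)
- probability of being alive at week w: D = exp(-0.08 × w/52.18), which is 0.9291 at Week 48 and 0.8658 at Week 94

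Complete testing gives p^K × D: 0.673 at Week 48 (K = 4) and 0.493 at Week 94 (K = 7, last test at Week 84). The visit rule estimates (1 - R) × D.

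| s per year | R, Week 48 | Visit rule | Excess (points) | R, Week 94 | Visit rule | Excess (points) |
|---|---|---|---|---|---|---|
| 5% | 0.2678 | 0.680 | 0.7 | 0.4130 | 0.508 | 1.5 |
| 10% | 0.2606 | 0.687 | 1.4 | 0.3962 | 0.523 | 3.0 |
| 20% | 0.2468 | 0.700 | 2.6 | 0.3652 | 0.550 | 5.7 |

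Simulation with staggered data-cuts gives slightly less: 0.6-2.6 points at about one year, and 1.4, 2.8 and 5.5 points at 94 weeks. A death between the last visit and the cut counts, while survivors leave the risk set at that visit, and this pulls the estimate down a little.

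**Step 3: the last-test rule.** The same mechanism acts more strongly when survivors are censored earlier. With visits exactly on schedule, last-test censoring is 1.0, 1.3 and 2.3 points too low at 94 weeks for 5%, 10% and 20% stopping.

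Visit windows matter more. With ±5-day scatter, actual dates and data-cuts uniform over 26-130 weeks, the errors at 94 weeks against complete testing are:

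| s per year | Visit rule | Last-test rule |
|---|---|---|
| 0% | -0.9 | -2.8 |
| 5% | +0.8 | -3.2 |
| 10% | +2.1 | -3.8 |
| 20% | +4.9 | -4.8 |

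Patients tested early in a window are censored before events from the same nominal visit are dated, so the risk set is too small. Dating tests by schedule removes most of this. With a 78-week median, deaths at 10% of the event hazard and 10% stopping, the last-test rule at Week 104 gives 0.381 against 0.413 on actual dates (-3.2 points). On scheduled dates it gives 0.407 against 0.416 (-0.9), while the visit rule gives 0.458 (+4.2). If faster progressors stop testing more often, the visit rule's excess grows and last-test censoring is nearly unbiased.

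**The case against.** The strongest reply is that the phrase is undefined and, beside an endpoint built on FVC and 6MWD, may mean the last efficacy assessment. That is possible but strained: the same sentence governs survival, where a test date has no meaning, and Table 4 names the tests when it means them. On either reading the text needs settling.

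Other parts of the reply stand and limit the point:

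- A reader might infer that every progression-free patient is affected. Table 4 already covers withdrawals and transplants.
- A reader might infer that each infusion visit without a test inflates the result, or that a missed test makes progression unobservable. Step 1 rules out the former. For the latter, a patient below the saturation threshold misses only the walk and can still progress on FVC; one with unusable spirometry can still progress on 6MWD; either can die. The full effect needs both tests missing.
- A reader might infer that the error always favours longer progression-free time and that last-test censoring cures it. With scattered visits on actual dates neither is true: the visit rule is slightly low when all tests are done, and last-test censoring is further from the truth at 0-10% stopping. This is an argument for scheduled dates, not for the present rule.
- SAP section 2 plans no statistical tests, so no error rate or treatment comparison is at stake.

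**Conclusion.** The point holds for patients still on treatment who keep attending but miss both FVC and 6MWD. For them the general rule counts untested time as progression-free, and it conflicts with the Table 4 rule for withdrawals. Relative to complete testing, the overstatement is about 0.6-2.6 points at about one year and 1.4-5.5 points at 94 weeks.

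Those figures rest on assumed progression, death and test-loss rates, on visits kept to schedule and on test loss unrelated to progression. They would be larger if sicker patients stop testing, smaller if only one test is lost, and near zero if testing is complete. The documents do not support a claim of serious or universal bias. This is a short clarification that should be made before the analysis of a descriptive endpoint.

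**What to change.** In SAP 5.4.1, split the general sentence by endpoint.

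For time to progression:

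- Censor event-free patients at the last evaluable progression assessment, in line with Table 4, or at Day 1 if there is none after baseline.
- State whether that assessment needs both FVC% predicted and 6MWD or either one. Table 4 joins them with *and*; an either-test rule would leave a patient who misses only the walk censored at the same 12-weekly visit.
- Date events and censoring by scheduled test date, or use an interval-censored method.
- State how a death after one or more missed tests counts.
- Report the last-visit rule as a sensitivity analysis.

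For survival, give a separate censoring date.

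The cost is a short SAP edit and one extra output. Progression-free figures may become slightly less favourable, and a small downward bias remains from deaths after the last test.

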5.7 ADVERSE EVENTS THAT OCCUR AFTER THE ADVERSE EVENT REPORTING PERIOD

After the end of the adverse event reporting period (defined as 8 weeks after the final dose of study drug), all deaths, regardless of cause, should be reported through use of the Long-Term Survival Follow-Up eCRF.

In addition, if the investigator becomes aware of a serious adverse event that is believed to be related to prior exposure to study drug, the event should be reported through use of the Adverse Event eCRF. However, if the EDC system is not available, the investigator should report these events directly to the Sponsor or its designee, either by faxing or by scanning and emailing the paper Clinical Trial Serious Adverse Event/Adverse Event of Special Interest Reporting Form using the fax number or email address provided to investigators.

5.8 EXPEDITED REPORTING TO HEALTH AUTHORITIES, INVESTIGATORS, INSTITUTIONAL REVIEW BOARDS, AND ETHICS COMMITTEES

The Sponsor will promptly evaluate all serious adverse events and adverse events of special interest against cumulative product experience to identify and expeditiously communicate possible new safety findings to investigators, IRBs, ECs, and applicable health authorities based on applicable legislation.

To determine reporting requirements for single adverse event cases, the Sponsor will assess the expectedness of these events through use of the reference safety information in the document listed below:

- PRM-151 Investigator's Brochure

The Sponsor will compare the severity of each event and the cumulative event frequency reported for the study with the severity and frequency reported in the applicable reference document.

Reporting requirements will also be based on the investigator's assessment of causality and seriousness, with allowance for upgrading by the Sponsor as needed.

The suspected unexpected serious adverse reaction (SUSAR) reporting will be as per the national regulatory requirements in participating countries in accordance with the Sponsor's internal standard operating procedures.

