Appendix 2 Schedule of Activities for Cohort C

Assessment	Survival follow-up
Window	Every 6 months (±14 days)
Survival Status ^a	x

^a Following the last dose of study treatment, discontinuation of treatment, or if patient becomes pregnant, patients will enter the survival follow-up phase. Information on survival will be collected remotely every 6 months.

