1.2 STUDY DESIGN

This open-label extension (OLE) study is being conducted to confirm the long-term safety, efficacy, and pharmacokinetics of zinpentraxin alfa in the treatment of eligible patients with IPF. Eligible patients from the Phase II Study PRM-151-202 who have received the open-label zinpentraxin alfa will be enrolled into Cohort A and patients who have completed the Phase III Study WA42293 will be enrolled into Cohort B. Additionally, patients who have discontinued treatment from or have completed Study WA42293 and do not want to receive open-label zinpentraxin alfa in this study, will be invited to enroll in survival follow-up Cohort C. Patients in Cohort C will not receive any treatment and will not undergo any safety or efficacy assessments during the study (see [Figure 1](#)). Patients who discontinue treatment from Cohorts A and B will automatically transition to Cohort C for long-term follow-up, unless they withdraw consent from the study.

[figure not shown]
The study schema is shown in [Figure 2](#).

Figure 1 Cohort Allocation

^a Only Cohorts A and B receive active treatment.
OLE = open-label extension.

Figure 2 Study Schema

IV=intravenous; Q4W=every 4 weeks.
PRM-151 to be read as zinpentraxin alfa or rhPTX-2.

Patients meeting the eligibility criteria for the study will receive zinpentraxin alfa 10 mg/kg every 4 weeks (Q4W). Throughout the study, patients will be monitored for safety by collection of adverse events (AEs; both serious and non-serious) and by regular physical exam and safety laboratory assessments.

Efficacy will be evaluated through assessment of functional capacity as measured by forced vital capacity (FVC), 6-minute walk distance (6MWD), other pulmonary function tests (PFTs), and assessment of patients with respiratory events leading to hospitalizations, progression of disease, or acute IPF exacerbations.

Patient reported outcomes (PRO) will be assessed using the St. George Respiratory Questionnaire (SGRQ), University of California, San Diego Shortness of Breath Questionnaire (UCSD-SOBQ), and European Quality of Life Scale (EuroQol) 5-Dimension, 5-Level Questionnaire (EQ-5D-5L).

[figure not shown]

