Dyspnea, fatigue, and blood oxygen saturation levels (SpO₂) will be assessed based on measurements taken during the 6-minute walk test (6MWT). High-resolution computed tomography (HRCT) of the chest will be assessed for changes between Week 52 from Study WA42293 to Week 52 (OLE) and Week 104 (OLE). Treated patients will be followed-up until the end of the study period, unless the patient withdraws consent for follow-up or death occurs.

For all patients receiving anti-fibrotic therapy, the investigator should document the dose, frequency, and duration of the anti-fibrotic drug.

During the study, patients may initiate background therapy of pirfenidone or nintedanib, if determined to be clinically indicated by the investigator. The study investigator is required to document the specific reason for introducing anti-fibrotic therapy in patients who started the study not on anti-fibrotic therapy.

Approximately 600–700 patients are expected to enroll in the study. Patients will initially receive loading doses of either zinpentraxin alfa 10 mg/kg intravenous (IV) infusion and/or placebo over 50–70 minutes on Days 1, 3, and 5, then one infusion of zinpentraxin alfa Q4W until the end of the study. Patients previously on the placebo arm of Study WA42293 will receive zinpentraxin alfa in all three loading doses, whereas patients previously on the active treatment arm of Study WA42293 will receive zinpentraxin alfa for the first dose, followed by placebo doses at the second and third loading dose visit. The loading doses will be blinded for Cohort B, to ensure that the blind in Study WA42293 is maintained for patients, site staff, and the Sponsor (see [Figure 3](#)).

Figure 3 Initial Loading Doses for Cohorts A and B

PRM-151 to be read as zinpentraxin alfa.

Patients entering Cohort A, from Study PRM-151-202, will have an eligibility visit prior to commencing dosing. The eligibility visit can occur on the same day as the dosing visit, if the patient is confirmed to be eligible for the study.

Patients entering Cohort B, from Study WA42293, will have their end-of-WA42293-study visit at Week 52. All assessments from the Week 52 Study WA42293 visit must be completed prior to commencing dosing in the OLE study. Ideally, patients will be enrolled into Cohort B on the same day as their Week 52 (Study WA42293) visit.

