	HRCT-evaluable	All enrolled patients who received at least one administration (full or partial dose) of study drug and have an OLE baseline and at least 1 post-baseline assessment.
	PK-evaluable	All enrolled patients who received at least one administration (full or partial dose) of study drug and have at least one evaluable post-dose PK sample that is above the lower limit of quantification and with sufficient data to determine plasma concentrations of zinpentraxin alfa at specified timepoints, unless major protocol deviations or unavailability of information (e.g., exact blood sampling time) occurred which may interfere with PK evaluation.
Cohort A, B, C	Survival population	All patients that entered the study

FAS = full analysis set; HRCT = high-resolution computed tomography; PRO = patient-reported outcomes; PK = pharmacokinetic.

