5.1.1 Treatment/Patient Group Terminology by Cohort

The terminology of treatment/patient groups for each cohort under each analysis population is defined below:

Cohort A

- zinpentraxin alfa: all data for all patients

Cohort B

- Placebo: all data for patients as assigned to placebo during analysis in the parent study (actual or planned, depending on the type of the analysis)

- Zinpentraxin alfa: all data for patients as assigned to zinpentraxin alfa during analysis in the parent study (actual or planned, depending on the type of the analysis)
- All patients

Survival population for Cohort C

- From Cohort A: survival data from patients that discontinued or died from Cohort A
- From Cohort B: survival data from patients that discontinued or died from Cohort B for the following treatments
 - Placebo: survival data for patients as assigned to placebo during analysis in the parent study (planned treatment)
 - Zinpentraxin alfa: survival data for patients as assigned to zinpentraxin alfa during analysis in the parent study (planned treatment)
 - All patients
- Directly from Study WA42293: survival data from patients that have discontinued from study treatment or have completed Study WA42293 and have not wanted to receive open-label zinpentraxin alfa.
 - Placebo: survival data for patients as assigned to placebo during analysis in the parent study (planned treatment)
 - Zinpentraxin alfa: survival data for patients as assigned to zinpentraxin alfa during analysis in the parent study (planned treatment)
 - All patients

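### The only specified survival curve for treated Cohorts A and B stops at treatment withdrawal, so survival time and deaths collected afterwards in Cohort C do not enter it

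*SAP*

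**What the plan says.** SAP 5.4 places survival among the efficacy analyses on the full analysis set (FAS) of Cohorts A and B. SAP 5.4.1 specifies Kaplan-Meier estimation from Day 1 of the extension (OLE). For treatment withdrawal, the survival row of Table 4 reads: "Any patients who withdraw from treatment will be censored at the date of withdrawal (hypothetical strategy". The same row censors at lung transplantation. For the remainder, "patients without an event will be censored at the last clinic assessment".

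Data collection goes further. SAP 1.2 says "Treated patients will be followed-up until the end of the study period", barring death or withdrawn consent, and that patients who stop treatment in Cohort A or B "will automatically transition to Cohort C for long-term follow-up". Protocol Appendix 2 adds: "Information on survival will be collected remotely every 6 months". Once the adverse event reporting period has ended, 8 weeks after the final dose, Protocol 5.7 says "all deaths, regardless of cause, should be reported through use of the Long-Term Survival Follow-Up eCRF".

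Three other places in the SAP touch on survival:

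- Table 2 defines a Survival population for Cohorts A, B and C: "All patients that entered the study".
- SAP 5.1.1 defines reporting groups for each cohort.
- SAP 5.3.2 plans a summary and a listing of deaths.

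**The concern.** The endpoint is named as survival measured by all-cause mortality, but the curve answers a narrower question: mortality while patients remain on treatment. Protocol 3.3.2 gives survival data as part of the reason for the design. Protocol 3.3.3 says survival will still be collected from patients who cannot or will not continue. SAP 5.1 expects most Cohort C patients to have contributed to Cohort A or B as well. The study thus collects what is needed for whole-cohort survival, and the plan specifies no estimate that uses it.

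The gap opens as soon as treatment stops. A patient who withdraws and dies within 8 weeks of the last dose is a reported death under Protocol 5.4.5.8, but is censored alive in the survival curve. The study is descriptive, so the estimate itself is the result: what is at stake is the reported long-term survival figure and its precision, not a test.

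**Working it through.** **Text.** A death after withdrawal falls after the Table 4 censoring date and cannot be an event. Changing that rule alone would not bring Cohort C follow-up in. Contact there is remote (Protocol 5.3.4), so survivors would still be censored at their last clinic assessment.

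No other part of the SAP fills the gap:

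- The Survival population in Table 2 has no estimator, time origin or censoring rule.
- In SAP 5.1.1, the sub-groups from Cohorts A and B listed for Cohort C hold only patients who discontinued or died. Patients alive on treatment are missing, so these sub-groups cannot give a treated-cohort curve.
- The main groups do hold everyone (for Cohort A, "zinpentraxin alfa: all data for all patients"), but the survival analysis specified for them is the one in Table 4.
- SAP 5.3.2 gives counts and a listing.

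**Size.** The documents state no figure to reproduce, and they give no discontinuation rate or mortality after stopping. Everything below is illustrative.

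Inputs: on-treatment death hazard h; discontinuation hazard d = 0.10 or 0.20 per year; post-stopping hazard k·h with k = 0.5, 1 or 2; t = 3 years. All are assumptions.

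- Planned Kaplan-Meier: exp(-ht).
- Whole-cohort survival: S(t) = exp(-(h+d)t) + d·[exp(-kht) - exp(-(h+d)t)] / (h + d - kh).
- Deaths the plan counts: h/(h+d)·[1 - exp(-(h+d)t)]. Omitted deaths: 1 - S(t) minus this.

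Example, h = 0.10, d = 0.20, k = 2:

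- Planned mortality: 1 - exp(-0.30) = 25.9%.
- S(3) = 0.4066 + 0.20 × (0.5488 - 0.4066)/0.10 = 0.691, so whole-cohort mortality is 30.9%.
- Counted: (0.10/0.30) × 0.5934 = 19.8 per 100. Omitted: 11.1 per 100, or 36% of deaths.

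A simulation of 400,000 patients gave 25.8%, 30.9% and 36%.

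Grid 1 takes h = 0.06 and 0.10. Grid 2 solves h so that whole-cohort median survival is 2 or 5 years. That is the background range in Protocol 3.3.3, which states no time origin; it is taken here from OLE Day 1. Cohort B has already completed 52 weeks, so Grid 1 covers lower hazards.

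| k | Grid 1: planned mortality | Grid 2: planned mortality | Share of deaths omitted |
|---|---|---|---|
| 0.5 | 1.1 to 2.9 points too high | 2.2 to 5.6 points too high | 7 to 14% |
| 1 | no difference | no difference | 11 to 24% |
| 2 | 1.9 to 5.0 points too low | 3.0 to 6.8 points too low | 17 to 37% |

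The extremes both come from a 2-year median with d = 0.20: 68.4% planned against 62.8% (k = 0.5), and 59.5% planned against 66.2% (k = 2; 6.8 points before rounding). At k = 1, losing 11 to 24% of deaths widens an interval by roughly 6 to 15% (1/√0.89 to 1/√0.76). Wider assumptions (withdrawal of 10 to 30% per year, k from 1 to 3) give differences of up to 16 points, which shows how little the documents fix the size.

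**The case against.** The strongest reply is that the estimand is declared and consistent. The objective concerns efficacy of the dosing regimen. Table 3 also uses a hypothetical strategy for permanent discontinuation, and Tables 4 and 5 censor at withdrawal throughout. This stands as a reason to keep the on-treatment analysis. It does not supply an all-cause survival estimate for the treated cohort.

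Second, later deaths remain visible. A reader might infer that they are lost or hidden; the documents do not support that. They can appear in Cohort C outputs and in the death summary and listing. What is missing is a specified estimate that includes them.

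Third, a reader might infer that the plan makes survival look better than it is. That is not supported either. Protocol 4.6.1 lists medical conditions and best-interest decisions among reasons to stop, but also pregnancy, hypersensitivity and infusion reactions. The documents give no mortality after stopping.

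Fourth, the omitted-death figures assume that every patient who stops is followed to year 3. Patients may decline Cohort C or withdraw consent (Protocol 4.6.1, 4.6.2), so the figures are upper limits for the rates used. This stands.

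Fifth, simply counting every known death would bring its own bias. A registry extends follow-up only for those it finds dead, while unmatched survivors stop at last contact. In a simulation with h = 0.10 and d = 0.20, this inflated 3-year mortality by about 1 to 2 points when 20 to 40% of patients who stopped could be reached only by registry. This stands and shapes the fix.

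Nor does the SAP contradict the protocol. Protocol 6.4 plans Kaplan-Meier for time to death and sets no censoring rule.

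**Conclusion.** The point holds and should be fixed. The one survival estimate specified for treated Cohorts A and B is on-treatment mortality, and no planned estimate uses the survival time and deaths collected after stopping. The reading of the text is firm. The size is not: under the stated assumptions the 3-year difference runs from 5.6 points of overstated mortality, through zero, to 6.8 points understated, with neither sign favoured by the documents. Even where there is no bias, up to 11 to 24% of deaths and some precision are given up. With no tests planned, no inference changes; the reported long-term survival does.

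**What to change.** In Table 4, for the Cohort A and B FAS:

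- **Main all-cause analysis.** Use a treatment-policy strategy for treatment withdrawal, from OLE Day 1, counting deaths found through Cohort C follow-up.
- **One cutoff.** Before each data cut, run a vital-status sweep using the existing Cohort C contacts. Count deaths up to the cutoff and censor patients confirmed alive at the cutoff. Censor patients without confirmed status at the date last known alive, a type of date SAP 5.5.1 already uses, and do not count their later registry-only deaths.
- **Registry deaths.** Put registry-only deaths in a sensitivity analysis. Count them in the main analysis only if registry-searched patients not found dead are censored at the search date.
- **Supplementary analysis.** Keep the censor-at-withdrawal version, labelled on-treatment.
- **Transplantation.** Keep censoring at recorded transplant dates, in line with the objective's exclusion of transplantation. State that transplants after entry to Cohort C may not be captured: Appendix 2 schedules survival status only, and the transplant assessment sits in Appendix 1. Add a sensitivity analysis that counts all deaths regardless of transplant.
- **Cause-specific mortality.** Leave IPF-related and respiratory-related mortality on-treatment and label them so, because Cohort C deaths are not adjudicated (SAP 1.2.2.4).

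The cost is SAP wording, a dataset derivation, the timing of the sweep and one added sensitivity analysis (a second if registry-only deaths are used). No new visits are needed, since the contacts and the survival eCRF exist. An entry in SAP Appendix 1 is optional. The remaining weakness is incomplete vital status for patients who decline Cohort C or withdraw consent; the report should state how many there are.
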